1.0 INTRODUCTION

Surgical Site Infection (SSI) is a major source of morbidity in both colorectal (CRS) and hepatopancreatobiliary (HPBS) surgery. The SSI rate has been published to be between 20-35% [1-3]. Specifically, colectomy for the treatment of colorectal cancer is associated with a SSI rate of 10-30% [1] and hepatectomy for hepatocellular carcinoma has a SSI rate of 15-25% [4, 5]. Pancreaticoduodenectomy for pancreatic adenocarcinoma has a SSI rate of 10-20% [2, 6]. Taken together, up to a third of patients undergoing these complex abdominal surgeries will suffer the additional morbidity of SSI despite interventions such as appropriately timed and selected antibiotics. This added level of morbidity increases the complexity of patient care during recovery from surgery, lengthens post-operative hospitalizations and adds significant overall medical costs. Given these persistently high rates of SSI despite best practice standards, a low morbidity intervention such as the incisional wound vacuum assisted closure (V.A.C) system is an attractive technology to try to further improve SSI rates in these patients.

V.A.C® technology or negative pressure wound therapy (NPWT) has revolutionized the management of complex open wounds but its role in closed wounds remains undefined. Initial enthusiasm for its potential role in reducing SSI rates in closed laparotomy wounds came from a report in the cardiothoracic literature performed as a collaboration between Duke University Medical Center (DUMC) and the Durham VA Medical Center [7]. Negative pressure wound therapy was applied to closed sternotomy wounds in 57 patients, with a 3% expected SSI rate. No sternal wound infections were seen in any patients. Though this initial report had small numbers of patients, the potential for this low morbidity technique to decrease SSI in sternotomy wounds was seen.

Several reports have investigated the preoperative patient-specific risk factors as well as surgically-related risk factors to predict risk of developing SSI [8]. However, there is no reported study in the medical literature indicating the role or efficacy of either conventional wound care with sterile dressings or the application of V.A.C.® to postoperative abdominal incisions in preventing SSI. However, both methods of wound care are employed on a daily basis in Duke University hospital system (DUMC, Duke Raleigh Hospital and Durham Regional Hospital) as well as other academic and private hospitals across the country. The conventional approach to postoperative surgical wound care has little evidence-based data to support its practice and surgeons have been using incisional V.A.C.® technology for several years in an attempt to curtail SSI in high risk patients.

2.0 NPWT SYSTEMS

2.1 PREVENA INCISION MANAGEMENT SYSTEM

The Prevena Incision Management System (PIMS) is the first battery powered negative pressure product designed specifically for management of closed surgical incisions that continue to drain following sutured or stapled closure. The PIMS covers and protects the incision from external infectious sources, while negative pressure removes fluid and infectious material from the surgical incision.

The Prevena System accomplishes its intended purpose by means of a dressing that seals the area around the incision site. This dressing is fitted with connections for fluid/air lines that provide the means of communication between the wound and the suction apparatus. The pump creates

a negative pressure (vacuum) of -125 mmHg relative to the wound and causes wound exudate to be pumped into the collection canister as necessary.

PIMS consists of:

- a small, portable, battery-powered suction pump,
- a canister for the collection of wound fluids, and
- a sterile, single use dressing kit.

PIMS-associated dressings include either the Peel and Place Dressing or the Customizable Dressing.

The PIMS Peel and Place dressing is an integrated, one-piece dressing comprised of a polyurethane film with acrylic adhesive that provides adhesion of the dressing to the skin surrounding the incision and a polyurethane shell that encapsulates the foam bolster and interface layer, providing a closed system. The polyurethane foam has a pore size of 400-600 microns and a violet colorant. Additionally, the dressing has a built-in pressure indicator, which shows when system pressure is at an acceptable level, and a skin interface layer with 0.019% ionic silver, which wicks fluid from the skin surface. The silver is not intended to treat infection but to reduce potential for contamination of the skin interface layer with microbes. This type of Prevena™ Incision Management System is a 510(k) – cleared, Class II device (K100821).

The Prevena Incision Management System with Customizable Dressing (Prevena Customizable) provides a new dressing configuration that has been designed to allow the clinician to cut the dressing to fit the incision size and geometry. The skin contacting dressing components include:

- a foam bolster with a skin interface layer,
- a hydrocolloid ring that is attached to the foam bolster to assist dressing application and to help reduce dressing leaks,
- hydrocolloid sealing strips for bridging foam dressing pieces, and
- a polyurethane film (V.A.C. Drape).

This product was recently cleared under 510(k) K121883.

PIMS is intended to manage the environment of surgical incisions that continue to drain following sutured or stapled closure by maintaining a closed environment and removing exudate via the application of negative pressure wound therapy. The Prevena System is intended to be applied to the wound site immediately after surgery, and continue for a minimum of 2 days up to a maximum of 7 days, depending on the surgeon's preference.

2.2 ACTIV.A.C. THERAPY UNIT

The ActiV.A.C. therapy unit can be used in special situations in which the incision is larger or has an unusual shape. It is also intended to manage the environment of surgical incisions that continue to drain following sutured or stapled closure by maintaining a closed environment and removing exudates via the application of negative pressure wound therapy. The unit is lightweight and portable to help patients resume their activities of daily living while still receiving the benefits

of V.A.C.® Therapy. The ActiV.A.C. can be used with the Prevena Peel and Place dressing and the Customizable dressing.

The ActiV.A.C unit consists of:

- a small, portable, battery-powered suction pump,
- a canister for the collection of wound fluids,

The ActiV.A.C. is a 510(k) – cleared, Class II device (K120033).

3.0 STUDY RATIONALE

Patients undergoing colorectal (CRS) and hepatopancreatobiliary (HPBS) surgery are at high risk for postoperative complications such as SSI and wound dehiscence. Such complications increase the complexity of patient care during recovery from surgery, lengthen post-operative hospitalizations, add significant overall medical costs and may potentially diminish quality of life and economic livelihood. To date, there is no reported study to evaluate the efficacy of either conventional wound care with sterile dressings or the application of V.A.C.® to postoperative abdominal incisions in preventing SSI. Furthermore, there are currently no identifiable additional risks for receiving either conventional wound care or PIMS. Therefore, the proposed study will compare SSI rates for subjects receiving NPWT via PIMS or ActiV.A.C to conventional wound care with sterile dressing.

We hypothesize that incisional NPWT via PIMS or ActiV.A.C.(Kinetic Concepts USA, Inc., San Antonio, TX) compared to conventionally closed laparotomy wounds may decrease the SSI rate in these subject populations which are associated with a high rate of postoperative wound complications.

4.0 STUDY OBJECTIVES

4.1 PRIMARY

- To compare the incidence of SSI rates between conventional wound care versus the incisional NPWT via PIMS or ActiV.A.C. within CRS or HPBS-associated laparotomy wounds as assessed on postoperative day 4-5 and the first postoperative clinic visit.

4.2 SECONDARY

- Characterize the incidence of SSI as superficial incisional, deep incisional, and organ/space as defined by The American College of Surgeons National Surgical Quality Improvement Program (NSQIP) guidelines.
- Assess (or compare) the length of hospital stay between subjects who receive standard of care and incisional NPWT via PIMS or ActiV.A.C.

5.0 STUDY DESIGN

5.1 STUDY DESCRIPTION

This study is a multi-center, open-label, randomized clinical trial conducted at Duke Cancer Institute and Indiana University to evaluate whether incisional NPWT can help reduce the rate of SSI in patients undergoing either colorectal or hepatopancreatobiliary surgery. Up to 170 subjects will be randomized in a 1:1 ratio to either conventional wound care (control group) or the incisional NPWT (experimental group) to ensure 138 evaluable subjects.

The primary study endpoint will be SSI within the laparotomy wound, as assessed on postoperative day 4-5 and the first postoperative clinic visit, which is anticipated to be within 30 days of surgery. Evaluable subjects are defined as those who have been randomized and completed both postoperative assessments. Non-evaluable subjects are those subjects who were randomized but did not complete both post-op visits. Non-evaluable scenarios include aborted surgeries, cancelled surgeries, death unrelated to study, and early device removal related to device malfunction. Screen failures are defined as those subjects not randomized.

Safety endpoints will be adverse events related to the device or dressing, including the presence of any abnormal skin findings (such as blisters or rash). These endpoints will be assessed from the day of surgery through the 30-day follow-up visit.

Subjects randomized to conventional wound care (control group) will have their skin incisions closed with skin staples, sutures, or surgical glue (per judgment of the treating physician), covered with sterile medical gauze and a form of adherent (tape or clear adhesive) for which the subject does not have any allergy. This dressing will be removed per the treating physician's discretion or institutional standards.

Subjects randomized to the incisional NPWT (experimental group) will have their skin incisions closed with skin staples or sutures (per judgment of the treating physician), a layer of non-adhesive dressing (Adaptic: Johnson & Johnson, New Brunswick, New Jersey) will cover the skin staples or sutures, followed by placement of an adhesive (Benzoin: generic), a Prevena™ Incision Management System peel and place or customizable dressing (KCI USA, Inc, San Antonio, Texas) covering only the skin staples or sutures. Please note, surgical glue should not be used for the experimental group. NPWT will be delivered using either the Prevena pump or the ActiV.AC. The incisional NPWT will then be continued for a minimum of 2 days up to a maximum of 7 days depending on physician preference.

Subjects will be clinically managed according to routine standard of care. Subjects will be assessed during their inpatient stay and at the time of routine postoperative clinic visits which is anticipated to be within 30 days of discharge. Presence or absence of SSI will be determined on postoperative day 4-5 and again at the time of the postoperative clinic visit, which is anticipated to be within 30 days of discharge. Criteria for determination of SSI are listed in Section 8.

Patients who are candidates for a laparoscopic approach will not be recruited. Note: patients scheduled for a staging laparoscopy followed by an open procedure are permitted to participate.

See Appendix 1 for the study schema.

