7.3.3 Post-op Visit Day 4-5

- Post-operative incision assessment
- Review of any side effects or symptoms
- This may be conducted by a review of clinical data
- PI will confirm the clinical data of any finding indicative of infection (i.e. redness, fever, positive culture)

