10.1 STATISTICAL ANALYSIS

The primary analysis will include all randomized and evaluable patients but exclude ineligible patients or patients who are canceled from the study before receiving any wound care. SSI is defined as an infection that occurs within 30 days of operation. The primary endpoint is the SSI rate. The primary analysis of comparing the conventional wound care (control group) and the incisional V.A.C® (experimental group) will be conducted using a chi-square test for two-sample binomial probabilities with a one-sided significance level of 0.1. The observed SSI rates and 90% Upper Confidence Bound (UCB) estimates will be reported. Preoperative, intraoperative, and postoperative variables will be tabulated and appropriate summary statistics will be reported. As a secondary analysis, comparison of treatment groups for SSI will be adjusted for any significant preoperative, intraoperative, or postoperative variables using logistic regression.

For secondary endpoints, the incidence of SSI as superficial incisional, deep incisional, and organ/space will be estimated along with the 90% UCBs. The secondary endpoint length of stay is a continuous variable. A Wilcoxon rank sum test will be used to assess the significance of the difference between groups in median length of stay. Median length of stay, its range and quartiles will be reported.

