11.0 INVESTIGATIONAL PRODUCT

The PIMS and ActiV.A.C. therapy units and associated dressings will be supplied by KCI.

Incisional NPWT will be removed prior to hospital discharge.

In the event that the clinician or study designee encounters issues with PIMS or control dressings prior to the desired time for removal, dressing replacement/reinforcement is acceptable but must be documented in the case report form (CRF). The PIMS unit may also be switched to use an ActiV.A.C unit. Any loss of negative pressure will be documented and will not determine subject evaluability. Please refer to the PIMS Instructions manual for guidance on operational questions.

A PIMS canister filled with 45 mL of wound fluid will lead to a “canister full” alarm.

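### The both-assessments rule can drop patients whose 30-day SSI status is already known, so the primary analysis can lose documented events

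*Combined protocol and SAP*

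**What the plan says.** Section 5.1 defines the set twice, once positively ("Evaluable subjects are defined as those who have been randomized and completed both postoperative assessments") and once negatively ("Non-evaluable subjects are those subjects who were randomized but did not complete both post-op visits"). It then gives examples: "Non-evaluable scenarios include aborted surgeries, cancelled surgeries, death unrelated to study, and early device removal related to device malfunction".

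Section 10.1 carries the definition into the primary analysis: "The primary analysis will include all randomized and evaluable patients but exclude ineligible patients". Patients cancelled before any wound care are also excluded. The same section fixes the endpoint: "SSI is defined as an infection that occurs within 30 days of operation".

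On ascertainment, Section 5.1 says "Presence or absence of SSI will be determined on postoperative day 4-5 and again at the time of the postoperative clinic visit". Sections 7.3.3 and 7.3.4 soften this for each assessment: "This may be conducted by a review of clinical data". The calendar in Section 7.1 places the later visit at day 30, plus or minus 14 days.

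The only other statement on evaluability is in Section 11.0: "Any loss of negative pressure will be documented and will not determine subject evaluability". It concerns device function and does not help a patient with a missed assessment. The plan has no missing-outcome rule, no analysis of all randomised patients and no sensitivity analysis for exclusions.

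**The concern.** The endpoint is a yes/no event over a fixed window. Once an SSI has been documented inside that window, nothing seen or missed later can change the answer. The evaluability rule ignores this and asks only whether both assessments took place.

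Three kinds of patient are affected:

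- One with an SSI on day 4-5 who dies, withdraws or is lost before the later assessment. Section 9.0 foresees all three.
- One with no day 4-5 data who is found at the later assessment to have had an SSI.
- One with no day 4-5 data whom the later assessment shows to be free of SSI. No event is lost here, but a usable outcome is.

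Inclusion therefore depends on survival, attendance and availability of records, all of which arise after randomisation. If these are related to SSI, the analysed rates are not those of the treated patients. If that relation also differs between the arms of this open-label trial, the comparison itself is distorted.

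The death example adds an inconsistency. The general rule makes any patient who dies before completing both assessments non-evaluable, while the example names only deaths unrelated to the study. The text does not settle how a related death is handled.

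**Working it through.** **Inputs.** From Section 10.0: control rate 17%, NPWT rate 5%, one-sided alpha 0.10, chi-square test, about 85% power, observed overall SSI rate 11%, and 14% ineligible or non-evaluable. From Section 5.1: 138 evaluable patients (69 per arm at 1:1) and up to 170 randomised.

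**Step 1: the plan's power.** With the pooled-variance test and no continuity correction,

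power = Phi{ [p1 - p2 - z(0.90) x sqrt(2 x pbar x (1 - pbar)/n)] / sqrt([p1(1 - p1) + p2(1 - p2)]/n) }.

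At n = 69 and pbar = 0.11: (0.12 - 1.2816 x 0.05327)/0.05228 = 0.99, so power is 83.9%. At 73 per arm (170 x 0.86 = 146) it is 85.4%. The stated 85% is reproduced.

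**Step 2: number of events.** 138 x 0.11 = 15.2. The design rates give the same total: 69 x 0.17 = 11.7 control and 69 x 0.05 = 3.5 NPWT. One lost event is 1/15.2 = 6.6% of the event count.

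**Step 3: power if k control events are dropped (k is assumed).** Observed control rate = (11.73 - k)/(69 - k), against 5% in 69 NPWT patients.

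| k | Control rate | Power |
|---|---|---|
| 0 | 17.0% | 83.9% |
| 1 | 15.8% | 78.8% |
| 2 | 14.5% | 72.5% |
| 3 | 13.2% | 65.1% |
| 4 | 11.9% | 56.3% |

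**Step 4: loss related to SSI, equal in both arms.** If SSI patients are dropped at an excess fraction f over other patients, observed rate = p(1 - f)/[p(1 - f) + (1 - p)]. Power is at 69 per arm.

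| f (assumed) | Control | NPWT | Power |
|---|---|---|---|
| 10% | 15.6% | 4.5% | 81.4% |
| 20% | 14.1% | 4.0% | 78.4% |
| 30% | 12.5% | 3.6% | 74.8% |

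Both rates and their difference shrink. Equal f applied to equal true rates gives equal observed rates, so this pattern creates no false difference. If 14% are lost whether or not they have an SSI, 0.17 x 0.86/(0.17 x 0.86 + 0.83 x 0.86) = 17%, and likewise 5% stays 5%.

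**Step 5: effect on a result.** z = (p1 - p2)/sqrt[pbar(1 - pbar)(1/n1 + 1/n2)], one-sided. The counts are illustrative; the first two blocks each start at or near 15 events.

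| Control | NPWT | What changed | p |
|---|---|---|---|
| 10/69 | 5/69 | start near the threshold | 0.086 |
| 10/69 | 6/70 | one NPWT SSI restored | 0.137 |
| 11/70 | 5/69 | one control SSI restored | 0.059 |
| 11/70 | 6/70 | one restored in each arm | 0.098 |
| 9/68 | 5/69 | one control SSI dropped from the start | 0.124 |
| 12/69 | 3/69 | start near the planned rates | 0.007 |
| 12/69 | 4/70 | one NPWT SSI restored | 0.016 |
| 12/69 | 5/71 | two NPWT SSIs restored | 0.030 |

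Near the threshold, one patient can move the result across 0.10 in either direction, depending on the arm. Near the planned effect, one or two do not.

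**The case against.** The strongest defence is that the set is prespecified, applies equally to both arms and follows the primary objective in Section 4.1, which names both time points. Because either assessment may be made from clinical records, a missed appointment need not be a missed assessment. That stands, and it lowers the likely number of lost patients. It does not alter the rule, and it cannot supply data that were never recorded.

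Several stronger readings are tempting, and the documents do not support them:

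- **That 14% (170 x 0.14 = about 24 patients) measures the loss.** Section 10.0 pools ineligible with non-evaluable patients, and the latter include cancelled and aborted surgeries. There is no split by reason, arm or SSI status.
- **That the rule removes the sickest and the fastest-recovering patients.** No discharge times or attendance figures are given.
- **That the rule favours NPWT.** The change from 0.086 to 0.137 needs a start near the threshold and a loss in the NPWT arm only. One event restored in each arm leaves p at 0.098, and one restored in control gives 0.059. Nothing in the documents points to losses in one arm.
- **That infection-related deaths are meant to be excluded.** The wording of the example suggests otherwise. What can be said is that rule and example disagree.

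A further fair objection concerns the remedy. Keeping incomplete patients only when they have an SSI would make inclusion depend on outcome and push the rates up. Nor can a later visit on day 16 (30 - 14) by itself settle a 30-day endpoint. Both objections stand, and the fix is built around them.

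**Conclusion.** The concern holds as a defect in the analysis set. Sections 5.1 and 10.1 together discard patients whose primary outcome is already documented, and no other part of the plan restores them.

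Its size is conditional. If one or two control events were lost at the design rates, power would fall from 83.9% to about 79% or 73%. A result near p = 0.10 could move either way on a single patient; a result near the planned effect would not. The number of patients affected and their arms are unknown, so one or two is an assumption and not an estimate.

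If missed assessments are unrelated to SSI and arm, only precision suffers. If they relate to SSI equally in both arms, both rates and their difference are understated. A spurious difference requires SSI-related loss that differs between arms. The plan specifies no report or analysis that would show which of these applies.

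**What to change.** Amend Sections 5.1 and 10.1 as follows.

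1. Define the primary analysis set as all eligible randomised patients whose incision was closed and dressed, analysed by assigned arm, whether or not both assessments were completed. Reword the list of non-evaluable scenarios to agree with this, and reconcile the death example with the general rule.
2. Count any SSI documented within 30 days of operation as an event, whenever and however it was found.
3. Count patients with no documented SSI as non-events, using all available clinical data through day 30. Keep those without a later assessment in the denominator, so that inclusion does not depend on outcome.
4. Report by arm and reason the number with incomplete follow-up: no later assessment, or a later assessment before day 30 with no further data.
5. Add two sensitivity analyses: one counting the incomplete patients without a documented SSI as SSI, and one restricted to patients with both assessments, which is the current rule.

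The cost is wording in two sections and one table, with no new visits, assessors or patients. The downside is small: for a few patients, absence of SSI rests on incomplete follow-up, which the first sensitivity analysis tests. Section 10.0 reports no statistical analysis of the endpoint so far, although the overall infection rate has been estimated. If that is still so, the change can be made before any comparison between arms is known.

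### Section 5.1 gives two answers on whether NPWT patients with early device removal for malfunction are analysed, and its both-assessments rule can delete a documented SSI

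*Combined protocol and SAP*

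**What the plan says.** **Primary set (section 10.1).** "The primary analysis will include all randomized and evaluable patients but exclude ineligible patients", together with "patients who are canceled from the study before receiving any wound care".

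**Evaluable (section 5.1).** "Evaluable subjects are defined as those who have been randomized and completed both postoperative assessments". The converse follows: "Non-evaluable subjects are those subjects who were randomized but did not complete both post-op visits". The next sentence is a list: "Non-evaluable scenarios include aborted surgeries, cancelled surgeries, death unrelated to study, and early device removal related to device malfunction".

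**Device problems (section 11.0).** "Any loss of negative pressure will be documented and will not determine subject evaluability". The same section allows the dressing to be replaced or reinforced and the pump to be switched.

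**Endpoint (section 10.1).** "SSI is defined as an infection that occurs within 30 days of operation".

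**Assessments (sections 7.3.3 and 7.3.4).** Both the day 4-5 and the day 30 (±14) assessment may be done by reviewing clinical data.

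**Design (section 5.1).** "This study is a multi-center, open-label, randomized clinical trial". Controls receive gauze with an adherent and have no device.

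The plan does not say who rules on evaluability or when. It states no missing-outcome rule, no sensitivity analysis of the analysis set, and no analysis of all treated patients by assigned arm.

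**The concern.** There are two separate defects in the definition of the primary analysis set.

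First, membership cannot be determined for an NPWT patient whose device is removed early for malfunction. The visit-based definition keeps a patient who completes both assessments; the list of scenarios drops the same patient. If the list governs, patients leave the comparison after randomisation for an event that cannot occur in the control arm. Because arm, and possibly outcome, may be known when the ruling is made, the choice between the readings is not protected.

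Second, one positive finding within 30 days establishes the endpoint, yet a patient must complete both assessments to be counted. A patient with an SSI confirmed on day 4-5 who then dies of an unrelated cause is non-evaluable, and the event disappears.

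About 16 events are expected in total, so a few patients moved in or out can decide a test at one-sided 0.1.

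**Working it through.** **1. Inputs from the documents.** SSI 17% (control) and 5% (NPWT), one-sided alpha 0.1, chi-square test, power about 85%, 170 randomised, 14% ineligible or non-evaluable, observed overall infection rate 11% (all section 10.0); 138 evaluable (section 5.1). 170 × 0.86 = 146, or 73 per arm; 138 is 69 per arm. I use 73 unless stated.

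**2. The plan's power.** With p̄ = 0.11, z = [0.12 − 1.2816·√(2·0.11·0.89/n)] / √[(0.17·0.83 + 0.05·0.95)/n].
- n = 73: (0.12 − 0.0664)/0.0508 = 1.055, power 85.4%.
- n = 69: 0.989, power 83.9%.

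Exact binomial enumeration of the same uncorrected test gives 87.8% and 86.3%. The stated figure reproduces. Expected events: 73 × (0.17 + 0.05) = 16.1, or 69 × 0.22 = 15.2.

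**3. Exclusion from the NPWT arm only.** The number dropped (k) and their SSI risk (p_m) are assumptions; the documents give neither. Take no true effect, 11% in both arms. Controls: n = 73 at 0.11. NPWT: n = 73 − k at retained rate (73·0.11 − k·p_m)/(73 − k). Example, k = 4 and p_m = 0.30: (8.03 − 1.20)/69 = 0.0990. Probability of declaring NPWT better, by exact enumeration (0.107 with no exclusions):

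| Dropped | 5% | 11% | 20% | 30% | 40% |
|---|---|---|---|---|---|
| 1 | 0.099 | 0.102 | 0.107 | 0.112 | 0.117 |
| 2 (2.7%) | 0.097 | 0.103 | 0.112 | 0.122 | 0.134 |
| 4 (5.5%) | 0.089 | 0.100 | 0.119 | 0.143 | 0.17 |
| 7 (9.6%) | 0.083 | 0.102 | 0.137 | 0.188 | 0.253 |

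Columns are the SSI risk in dropped patients. The 11% column differs from 0.107 only through discreteness at unequal sample sizes. The bottom-right cell is extreme: 0.40 against a retained rate of 0.079, about five times the risk.

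**4. Worked examples.** z = (x₁/n₁ − x₂/n₂)/√[p̄(1 − p̄)(1/n₁ + 1/n₂)].
- 11/73 v 5/73: z = 1.590, p = 0.056.
- Restore one patient with an SSI (6/74): p = 0.094, same conclusion.
- Restore two patients with 0, 1 or 2 SSIs (5, 6 or 7 of 75): p = 0.050, 0.089 or 0.143.
- Restore five with 0, 1 or 2 SSIs (5, 6 or 7 of 78): p = 0.042, 0.076 or 0.124.

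Here two restored SSIs are needed to change the result. In another example one is enough: 12/69 v 7/69 gives p = 0.108, and removing one NPWT patient with an SSI (6/68) gives 0.069.

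**5. Both-assessments rule, equal loss in both arms (assumed).** Start from 85 per arm and lose 10% of patients without SSI.
- 10% of SSI patients also lost: rates stay 17% and 5%, ratio 0.294, power 0.888.
- 20% lost: observed 15.4% and 4.5%, ratio 0.290, power 0.857.
- 30% lost: observed 13.7% and 3.9%, ratio 0.286, power 0.821.

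The ratio hardly moves; the loss is in events and power. The third decimal of power depends on how fractional sample sizes are rounded.

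**The case against.** A coherent benign reading exists. The list directly follows the sentence on missed visits and can be taken as examples of why visits are missed. Section 10.1 names its own further exclusions, and neither covers a treated patient whose device failed. Section 11.0 leans the same way, although loss of pressure and early removal are different events, so the firm inconsistency lies within 5.1. On this view one clarifying sentence would do.

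The size is also unproven. All malfunction inputs are assumed, one or two removals move the error only to between 0.097 and 0.134, and the large values need four to seven failures at high SSI risk. The deleted-SSI case is narrow: record review can complete most second assessments, leaving mainly deaths and patients with no later record.

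All of this is fair and limits the claim about bias. It does not settle who is analysed. Section 10.1 relies on the word evaluable, which leads back to the ambiguous list, and two analysts could follow the protocol and report different denominators. Record review makes lost SSIs rarer but leaves the rule in place, including for the unrelated deaths that 5.1 names.

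**Conclusion.** The concern holds and must be fixed. The primary analysis set cannot be determined from the text. One of its two readings removes NPWT patients only, after randomisation, and the evaluability rule can discard an event that already meets the endpoint definition. None of this depends on an assumed malfunction rate.

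Material bias is not shown, and its size and direction are unknown. If removed patients have above-average SSI risk, the exclusion favours NPWT; at average risk there is no inflation; at below-average risk it works against NPWT. With one or two removals the effect on the error rate is small. The both-assessments rule costs events and power but does not bias towards NPWT if loss is equal in both arms.

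**What to change.** **Must change**
- (a) Delete the malfunction scenario from 5.1 and align 5.1, 10.1 and 11.0. Analyse all randomised eligible patients who had the operation and received wound care, by assigned arm, regardless of malfunction or early removal. The existing exclusion in 10.1 of patients cancelled before any wound care stays.
- (b) Count SSI as present if documented at any time within 30 days of operation, whether or not both assessments were completed.

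**Supporting**
- (c) For patients with no recorded SSI and no second assessment in the 30 ± 14 day window, obtain status by the record review already allowed. Report a best/worst-case analysis for any still unknown; multiple imputation is optional.
- (d) Base ineligibility exclusions only on facts that predate randomisation.
- (e) Keep the present evaluable set as a sensitivity analysis.

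**Cost.** Wording in three sections and review of at most 0.14 × 170 = 23.8, about 24 charts; fewer in practice, because the 14% includes ineligible patients. Section 10.0 reports that the endpoint had not been analysed, so on that statement the rule can be set before results are seen.

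Keeping device failures dilutes the effect slightly. If k of 73 NPWT patients fail and carry 17% risk instead of 5% (assumed), the arm's rate is [0.05(73 − k) + 0.17k]/73. For k = 1, 2, 4, 7 this is 5.16%, 5.33%, 5.66%, 6.15%, and power falls from 0.878 to 0.868, 0.859, 0.838, 0.804.

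Best/worst-case bounds are informative only if few outcomes stay unknown. In the 11/73 v 5/73 example, one unknown per arm gives p from 0.036 (12/74 v 5/74) to 0.099 (11/74 v 6/74); two per arm give 0.022 to 0.157.
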